6.7 BASELINE, TIME WINDOWS AND CALCULATED VISITS

Study day will be calculated relative to the date of the first dose of the randomized treatment. The day prior to the date of the first administration of randomized treatment will be Day -1 and the date of the first administration of randomized treatment will be Day 1. Day 0 will not exist.

Unless otherwise specified, baseline is defined as the last measurement collected on or prior to the date and time of first treatment administration. If no measurements are collected for a particular variable on or before the date of first treatment administration, no baseline value will be derived for that particular variable. Per the CTP, for the ophthalmic endpoints, baseline is defined as the value at Visit 2a; if not measured at Visit 2a then baseline is the value at Visit 1.

To utilize all available data, including values collected between protocol-specified visit windows, the time intervals and descriptions shown in [Table 6.7: 1](#) will be used in the analysis of safety and efficacy data with the following exceptions. Adverse events and concomitant medications are also collected during phone visits 2b (Study Day 8 ± 1) and 4b (Study Day 83 ± 1). Sites in Spain have additional mandatory visits 3c and 4c during which AEs, concomitant medications, vital signs and laboratory data are collected. Separate interval mapping will be defined in [Table 6.7: 2](#) and [Table 6.7: 3](#), respectively, to accommodate these exceptions.

If multiple values are recorded within a visit interval, the value collected closest to the planned visit date will be included in analyses of efficacy endpoints and vital signs data. For all other safety data, the worst of multiple values within an analysis window will be selected for analysis (see guidance for Handling, Display and Analysis of Laboratory Data [\(6\)](#)). Only one observation per time window will be selected for analysis at an on-treatment visit.

Table 6.7: 1 Visit intervals for efficacy endpoints

		Interval Definition		
Visit	Planned day	From (day)	To (day)	Visit description
1	-28 to -3	NA	-1	Screening
2	1	1	1 ^b	Baseline ^c
3	29	2	43	Week 4
4a	57	44	71	Week 8
EOT	85	72	Date of drug intake at EoT visit + 14	Week 12
FU1	EOT +28	Date of drug intake at EOT visit + 15	Date of drug intake in EOT visit +34	Follow-up 1
FU2	EOT +56	Date of drug intake in EOT visit +35	Date of drug intake in EOT visit +62	Follow-up 2
FU3	EOT + 84	Date of drug intake in EOT visit +63	Last assessment date	Follow-up 3

b Day 1 is defined as the date of first treatment administration

c Baseline data must be collected before time of study drug administration during Visit 2.

Table 6.7: 2 Visit intervals for ECG, vital signs, and laboratory data

		Interval Definition		
Visit	Planned day	From (day)	To (day)	Visit description
1	-28 to -3	NA	-1	Screening ^a
2a	1	1 ^b (pre-dose)	1	Baseline ^{a,c}
2a	1	1 (post-dose)	14	Week 1 ^d
3	29	15	43	Week 4
4a	57	44	71	Week 8
EOT	85	72	Date of drug intake in EOT visit +1	Week 12
FU1	EOT +28	Date of drug intake in EOT visit +2	Date of drug intake in EOT visit +34	Follow-up 1 ^e
FU2	EOT +56	Date of drug intake in EOT visit +35	Date of drug intake in EOT visit +62	Follow-up 2
FU3	EOT + 84	Date of drug intake in EOT visit +63	Last assessment date	Follow-up 3

a Baseline ECG data are collected at screening visit.

b Day 1 is defined as the date of first treatment administration.

c Baseline data must be collected before time of study drug administration during Visit 2.

d Only measurements collected after drug administration at Visit 2a are considered Week 1 values.

e In case of premature treatment discontinuation FU starts at +1 day after last drug admin for these values.

Table 6.7: 3 Visit intervals for vital signs and laboratory data for patients from sites in Spain only

Interval Definition				
Visit	Planned day	From (day)	To (day)	Visit description
1	-28- -3	NA	-1	Screening
2a	1	1 ^a	1	Baseline ^b
2b	8	1 ^c	11	Week 1 (Day 8)
2c	15	12	22	Week 2 (Day 15)
3	29	23	40	Week 4 (Day 29)
3c	50	41	53	Week 6 (Day 50)
4a	57	54	70	Week 8 (Day 57)
4b	83	71	84	Week 11 (Day 83)
EOT	85	85	Date of drug intake in EOT visit +1	Week 12 (Day 85)
FU1		Date of drug intake in EOT visit +2	Date of drug intake in EOT visit +34	Follow-up 1 ^d
FU2		Date of drug intake in EOT visit +35	Date of drug intake in EOT visit +62	Follow-up 2
FU3		Date of drug intake in EOT visit +63	Last assessment date	Follow-up 3

a Day 1 is defined as the date of first treatment administration

b Baseline data must be collected before time of study drug administration during Visit 2.

c Measurements collected after drug administration at Visit 2a or at Visit 2b are considered Week 1 values.

d In case of premature treatment discontinuation FU starts at +1 day after last drug admin for these values.

[figure not shown]
There will be a centralized evaluation of 12-lead ECG recordings at the time points specified in [Table 6.7: 2](#). Three triplicate ECGs will be recorded as baseline prior to the first drug administration. The baseline value of an ECG variable is defined as the mean of these baseline ECG measurements.

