#### 5.2.4 Electrocardiogram

A centralized ECG assessment will be used for this study. Three ECGs are to be recorded as 12-lead ECGs by a qualified person at the visits outlined in the [Flow Chart](#) approximately 60 min after trial drug intake using equipment provided by a central ECG vendor. All ECGs will be printed locally and evaluated by the investigator or a designee; in addition, there is a central cardiologist over-read.

ECGs will be recorded for a 10-second duration after the patients have rested for at least 5 minutes in a supine position. Six limb leads, as specified by Einthoven (I, II and III) and Goldberger (aVR, aVL, aVF), and six pre-cordial leads (V1–V6), according to Wilson, will be used. ECGs will be recorded but records may be repeated for quality reasons and the repeated recording will be used for analysis. If necessary, additional ECGs may be recorded for safety reasons. Information about the details of ECG collection will be provided in the ISF.

All three ECGs at screening (used as baseline before the first drug administration), and only the first of the three replicate ECGs at a remaining time points will be evaluated (signed, dated and commented upon) by the treating physician/ investigator. The remaining second and third replicate ECGs will be printed and kept together with other medical records of the patient for additional analyses if required at a later time point.

All ECGs recorded during trial conduct including the baseline ECG will also be transmitted to a vendor for central evaluation and stored at an external central ECG database. Only the first of the three replicate ECGs at a single assessment time will be centrally evaluated and transferred to the sponsor. The results of the centralized evaluation will be sent from the ECG core lab to the sponsor according to a pre-specified data transmission agreement. The remaining second and third replicate ECGs will only be stored at the ECG vendor for additional analyses if required at a later time point.

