## **6.2.2 Treatment period(s)**

### General remarks

As soon as eligibility of enrolled patients is confirmed, patients may enter the study and Visit 2a can be conducted including randomization via IRT.

IRT should not be called in advance of Visit 2a until eligibility is fully confirmed, as randomization of a patient cannot be reserved.

Unscheduled visits will be possible at the discretion of the investigator at any time in order to check the safety of the patient including a potential worsening of ocular function or to perform safety laboratory assessments.

At every site visit during the treatment period (Visits 2a – EOT) patients are asked about their alcohol and caffeine consumption and information is recorded in the eCRF.

Trial drug diary

The patients will be instructed to complete trial drug diaries during the treatment phase to document date and clock time of drug intake at home between the on-site visits. If the trial drug was not administered as planned, the reason should be provided in the diary by the patient.

A new diary will be dispensed to the patients at every visit during the treatment period and will be collected at the following visit by the site (please refer to the [Flow Chart](#)). Selected entries, i.e. drug administration dates and times from the 3 days prior to each visit, will be entered in the eCRF by the site.

Visit 2a (Randomization)

At the start of Visit 2a it should be ensured that all Visit 1 procedures have been successfully completed within the past 28 days and eligibility has been confirmed including confirmation of eligibility by the CRC.

Trial medication is administered after predose blood collection. [REDACTED]

Trial drug kits will be dispensed for home administration, and a trial drug diary will be dispensed to the patients.

Visit 2b (Phone Visit)

This interim phone call will be performed one week after randomization in order to collect AEs, changes in concomitant therapy, and to check handling of the trial drug diary. Patients should be reminded not to take medication in the morning prior to the next visit.

Visits 3 and 4a:

At these visits the trial drug diary will be checked and dates and times of drug administration at the 3 days prior to the visits will be recorded in the eCRF. Unused trial medication, as well as empty blisters and packaging, will be collected.

Visit 4b (Phone Visit)

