7.8.3 Vital signs

Descriptive summaries of vital signs and body weight values over time and for the difference from baseline will be provided.

Clinically relevant findings in vital signs data will be reported as AEs and will be analyzed as part of AE analyses.

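### SAP 6.7 picks repeat safety values by data type, not by table purpose: worst laboratory and ECG values enter mean changes, and no visible table shows the highest blood pressure

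*SAP*

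**What the plan says.** SAP 6.7 sets two rules for several values in one visit window. For the first group of data, "the value collected closest to the planned visit date will be included in analyses of efficacy endpoints and vital signs data". For the rest, "For all other safety data, the worst of multiple values within an analysis window will be selected for analysis", with a reference to the sponsor's laboratory guidance (SAP reference 6). It adds: "Only one observation per time window will be selected for analysis at an on-treatment visit". Neither rule separates summaries of means from tables of abnormal values.

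The general definition is that "baseline is defined as the last measurement collected on or prior to the date and time of first treatment administration"; for ECG variables 6.7 uses the mean of the baseline recordings. Neither baseline is a worst value.

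On outputs:
- SAP 7.8.2 plans descriptive statistics and changes from baseline for laboratory data. Its reference-range tables use the last on-treatment value, and a further table counts potentially clinically significant abnormalities.
- SAP 7.8.4 plans descriptive statistics, changes over time and graphs of mean change for ECG.
- SAP 7.8.3 says: "Descriptive summaries of vital signs and body weight values over time and for the difference from baseline will be provided". It adds that clinically relevant vital-sign findings are reported as adverse events. No maximum or threshold table is visible.

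The protocol foresees repeats. Section 6.2.2 states: "Unscheduled visits will be possible at the discretion of the investigator at any time in order to check the safety of the patient". For ECG, protocol 5.2.4 states that "records may be repeated for quality reasons and the repeated recording will be used for analysis".

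**The concern.** A mean change and an abnormality table need different values. A mean needs one chosen without regard to its size; an abnormality table needs the extreme. SAP 6.7 fixes one choice per data type, so each type is served badly in one of its uses.

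For laboratory and ECG data, the extreme of several values is set against an ordinary baseline. That moves the mean change in one direction even with an inert drug, and moves the arm difference if one arm is retested more often. For ECG, a literal worst-value rule can also select a tracing that the protocol treats as replaced.

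For blood pressure, a high reading at an unscheduled visit normally loses to the scheduled reading nearer the planned day, and no other vital-signs table picks it up. The protocol gives some reason to want such readings displayed by arm. It restricts MAO inhibitors and sympathomimetics (4.2.2.1), advises against large amounts of tyramine-rich food (4.2.2.2), and lists a report of irreversible MAO-B inhibition in vitro (9.2). Safety and tolerability is the primary objective.

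**Working it through.** The plan gives no figure on this point. Repeat rates, SDs and the day of an unscheduled visit are assumptions below.

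**1. Unselective repeats, no drug effect.** With independent normal errors and within-patient SD σ, the expected worst of two values exceeds a single value by σ/√π = 0.564σ. For the worst of three it is 3σ/(2√π) = 0.846σ. The expected baseline is unaffected, so the whole excess enters the change. If a share f of an arm has one repeat in a window, its mean shifts by 0.564f:

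| f | shift in arm mean (σ) |
|---|---|
| 5% | 0.03 |
| 10% | 0.06 |
| 20% | 0.11 |
| 50% | 0.28 |

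The false arm difference is 0.564 × (difference in f):
- equal rates: 0
- 20% v 10%: 0.10 × 0.564 = 0.06σ
- 30% v 10%: 0.20 × 0.564 = 0.11σ

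**2. Repeats triggered by a high scheduled value.** Assume between-patient SD equal to within-patient SD (both 1). Given a scheduled value v, measured from the population mean, the repeat minus v is normal with mean −v/2 and variance 1.5. The added bias is the expected positive part of that difference, averaged over the patients who trigger a repeat.

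| trigger | per retested patient (σ) | arm mean (σ) |
|---|---|---|
| top 10% | 0.107 | 0.011 |
| top 20% | 0.157 | 0.031 |
| top 30% | 0.200 | 0.060 |

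Triggered rates of 30% v 10% give 0.060 − 0.011 = 0.049σ. The bias is smaller than under step 1 because the worst of the two is usually the scheduled value itself.

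**3. QTcF scale.** With an assumed within-patient SD of 5-12 ms, one unselective repeat adds 0.564 × 5 = 2.8 ms to 0.564 × 12 = 6.8 ms for that patient. At 30% v 10% the arm difference is 0.113 × 5 = 0.6 ms to 0.113 × 12 = 1.4 ms.

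**4. How often the closest-date rule passes over an unscheduled blood pressure.** Inputs are the windows in SAP Table 6.7: 2 (Week 4: days 15-43, planned day 29; Week 8: days 44-71, planned day 57) and the ±3-day visit window in the protocol Flow Chart. Assume the unscheduled day is uniform over the window and the scheduled day uniform over ±3 days.
- Week 4: 29 × 7 = 203 pairs. The unscheduled reading is further from plan in 172 (85%) and tied in 13 (6%).
- Week 8: 28 × 7 = 196 pairs. It is further in 165 (84%) and tied in 13 (7%).

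Sites in Spain use other windows (Table 6.7: 3) and are not covered by this count.

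**5. ECG passages side by side.** Protocol 5.2.4 makes a quality repeat the recording for analysis; SAP 6.7 takes the worst in the window without excluding replaced tracings. Protocol 5.2.4 also has only the first of three replicates centrally evaluated and transferred, while SAP 6.7 averages the baseline ECGs.

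**The case against.** The strongest reply is that little is lost. Safety analyses are descriptive with no hypothesis testing (protocol 7.3.4). Closest-date selection is right for the means in 7.8.3. All individual values are listed (SAP 7), and clinically relevant findings become adverse events. The SAP is not blind to purpose everywhere: 6.6 uses the maximum on-treatment QTc for new onset when baseline is missing, and 7.8.2 uses the last on-treatment value for reference ranges. The cited laboratory guidance may itself separate means from abnormality tables. On ECG, the SAP elaborates the protocol, so a replaced tracing may never be a candidate. All of this stands as a limit on size and certainty. It does not supply the missing wording or an arm-level display of high blood pressures, and a laboratory guidance would not obviously settle ECG.

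A reader might infer three stronger things that the documents do not support:
- That every unscheduled peak is lost. A reading is passed over only if another value is closer to plan, and it stays in the listings.
- That blood pressure is the one safety variable where peaks matter. The only adverse event of special interest is hepatic injury, which is defined by laboratory elevations.
- That retesting after a high value makes the bias worse than the unselective figure. Step 2 shows that it makes it smaller.

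**Conclusion.** The point holds as a modest, inexpensive improvement. Followed as written, SAP 6.7 puts a one-sided selection effect into laboratory and ECG mean changes. It is 0.56 within-patient SD per patient with one unselective repeat, and about 0.1-0.2 SD per retested patient when a scheduled value in the top 10-30% triggers the repeat. The arm difference is zero at equal repeat rates, 0.06 SD at 20% v 10%, and 0.11 SD at 30% v 10%, for unselective repeats. These sizes rest on normal, independent errors and assumed repeat rates; the triggered figures also assume equal between- and within-patient SDs. That the worst value feeds the laboratory means is the plain reading of 6.7 with 7.8.2, but reference 6 could not be checked and parts of the SAP are redacted.

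For vital signs the selection rule itself is sound for means. The gap is that no visible table uses the highest value. For ECG, the two documents need reconciling whatever the size of the bias. No test or sample size is affected; what changes is the safety tables, which matter in a trial whose primary objective is safety.

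**What to change.** In SAP 6.7, state the rule by purpose for laboratory, ECG and vital signs alike:

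- **(a)** By-visit means and changes use the value closest to the planned day, after removing tracings replaced for quality reasons under protocol 5.2.4.
- **(b)** Notable-value and potentially-clinically-significant tables use the worst of all valid post-dose values, scheduled or not, with the direction of worst stated for parameters that can be abnormal both ways. The reference-range table in 7.8.2, based on the last on-treatment value, stays as it is.

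Also state which ECG replicates form the baseline mean, consistently with what protocol 5.2.4 says is transferred.

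Add to SAP 7.8.3 one table by arm of each patient's maximum post-dose systolic and diastolic pressure. Include counts above the values in exclusion criterion 12 (systolic >180 mmHg; systolic >160 and/or diastolic >100 mmHg), labelled as single-reading counts, because that criterion requires two consecutive measurements for the second pair. They serve only as display cut-offs.

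The cost is SAP wording and one extra table, with no new data. The downside is that laboratory means would depart from the cited standard's single-value selection, which 6.7 should say openly.

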**FLOW CHART**

Tests and Procedures	Screening 	Treatment Period 						Follow-up period		
		1 	2a Base- line	2b Phone Visit	3	4a	4b Phone Visit	EOT 	FU1	FU2
Visit	1 									
Week			1	4	8		12	16	20	24
Day	-28 to -3 	1	8	29	57	83	85	EOT  +28	EOT  +56	EOT  +84
Time window for visits (days)			±1	±3	±3	±1	+6	±6	±6	±6
Informed consent signed 	X 									
Informed consent for biobanking 	X									
Demographics	X									
Medical history/baseline conditions	X									
Substance use 	X	X		X	X		X	X	X	X
Concomitant therapy	X	X	X	X	X	X	X	X	X	X
All AEs/SAEs/ AESIs 	X	X	X	X	X	X	X	X	X	X
Physical examination	X	X		X	X		X	X	X	X
Vital signs 	X	X		X	X		X	X	X	X
Height	X									
Body weight	X	X					X			X
Pregnancy testing 	X S	X U		X U	X U		X U	X U	X U	X U
Resting ECG 	X	X		X	X		X	X	X	X
Ophthalmological exams: 	X	X		X	X		X	X	X	X
Visual acuity (BCVA)										
Color fundus photography (for DRSS evaluation) 	X 	X		X	X		X	X	X	X
Gonioscopy	X									
In-/Exclusion criteria	X	X								
IRT call 	X	X		X	X		X			
Trial medication administration at site		X		X	X		X			
Dispense trial medication		X		X	X					
Collection of trial medication, check of medication compliance				X	X		X			
Dispense trial medication diary 		X		X	X					

Tests and Procedures	Screening 	Treatment Period 						Follow-up period		
	1 	2a Base- line	2b Phone Visit	3	4a	4b Phone Visit	EOT 	FU1	FU2	FU3
Collection / check of trial medication diary				X	X		X			
Reminder to the patient 			X			X				
Laboratory tests: Chemistry, hematology, urinalysis	X	X		X	X		X	X	X	X
Infection testing 	X									
[REDACTED]		■ ■		■ ■			■ ■			
[REDACTED]		■					■			■
[REDACTED]		■ ■								
[REDACTED]		■ ■								
Study completion 										X

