### **6.2.3 Follow up period and trial completion**

For all patients who had at least one dose of trial medication the follow-up visits FU1, FU2 and FU3 will be performed according to the [Flow Chart](#) 4, 8 and 12 weeks after the last intake of trial drug, respectively. If the last day of trial drug intake is different from the EOT visit, the date of the last day of trial drug intake will be used for calculation of the FU visit dates.

Should it be not possible for the patient to attend a follow up visit at the study site, a visit out of time window should be performed as soon as possible; if a visit at the site is not possible at all, at least a phone contact should occur at the scheduled visit time point.

In case that standard of care DR treatment is administered at these visits, this has to be documented in the eCRF.

The FU3 visit is the final visit and the Study completion page in the eCRF has to be entered.

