6.6 HANDLING OF MISSING DATA AND OUTLIERS

Techniques for handling missing data are described in Section 7.5 of the CTP. Missing and incomplete adverse event dates will be handled according to BI standards (5). The handling of missing PK data and values reported as NOS, NOR, NOA or BLQ are described in Section 10.1 of the CTP.

For efficacy analyses, missing data will not be imputed. Mixed effect models will handle missing data based on a likelihood methods under the “missing at random” assumption. No imputations of missing AEs, laboratory data or vital signs data are planned. For binary efficacy endpoints, patients with missing data in the study eye at the time point of interest will be considered non-responders, i.e. failure to achieve the defined endpoint.

For ECG data, if single cardiac cycles of an ECG (out of three) are missing, the arithmetic mean for this single ECG will be calculated with the reduced number (1 or 2) of cycles.

For the classification of the on-treatment QTc/QT intervals into ‘no new onset’ / ‘new onset’ categories, a missing value is obtained only in the case that

- i. all on-treatment values are missing, and
- ii. the baseline value is less than or equal to 500 msec, or missing.

If condition (i) is fulfilled but the baseline value is greater than 500 msec, this case will be categorized as ‘no new onset’. If baseline is missing and the maximum on-treatment QTc interval is greater than 450 msec (or 500 msec for QT interval, respectively), this is classified as a ‘new onset’ in the respective category. If baseline is missing and the maximum QTc interval is less than or equal to 450 msec (or 500 msec for QT interval, respectively), this will be categorized as ‘no new onset’. If baseline is missing, a QTc/QT interval > 500 msec at any time on treatment will be a notable finding.

For patients on active drug, missing plasma concentration values with ‘BLQ’ in the comment field will be replaced by $\frac{1}{2}$ LLOQ.

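### SAP follow-up windows for FU1 and FU2 close at the protocol's +6-day tolerance rather than midway between visits, so a visit 7 to 14 days late is filed under the next visit

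*SAP*

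**What the plan says.** Protocol Section 6.2.3 places FU1, FU2 and FU3 "4, 8 and 12 weeks after the last intake of trial drug, respectively", that is at +28, +56 and +84 days. The Flow Chart gives each a tolerance of ±6 days. Late visits are foreseen: if a patient cannot attend, "a visit out of time window should be performed as soon as possible". Protocol Section 6.1 asks that later visits stay on the original schedule.

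SAP Section 6.7 introduces its analysis windows with this purpose: "To utilize all available data, including values collected between protocol-specified visit windows". Tables 6.7: 1 (efficacy), 6.7: 2 (ECG, vital signs, laboratory) and 6.7: 3 (vital signs and laboratory, Spanish sites) then give the same follow-up limits. FU1 ends at "Date of drug intake in EOT visit +34", FU2 starts at "Date of drug intake in EOT visit +35" and ends at +62, and FU3 runs from +63 to the last assessment.

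When several values fall in one window, "the value collected closest to the planned visit date will be included in analyses of efficacy endpoints and vital signs data". Laboratory and ECG values come under a different rule, which covers the remaining safety data and takes the worst value in the window.

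**The concern.** The follow-up limits work against the purpose the SAP gives for having windows. A value taken just outside the FU1 protocol window is the kind of in-between value the windows are meant to keep. It is instead assigned to a visit whose planned day is much further away.

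The 12-week follow-up was included because binding to the target is irreversible and prolonged effects should be observable (Protocol Section 1.4). The time course over FU1, FU2 and FU3 is therefore of interest in its own right. Misfiled values blur it: one visit looks empty, and the next either ignores the late value or shows it at the wrong time.

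**Working it through.** **Inputs.** Planned days +28, +56 and +84 (Protocol 6.2.3); tolerance ±6 days (Flow Chart); SAP limits +34 and +62 (Tables 6.7: 1 to 6.7: 3); treatment visits at Days 29, 57 and 85 (Table 6.7: 1). Days are counted from the dose at the EOT visit. For a patient who completes treatment as scheduled, this is also the last intake.

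**Where the SAP limits come from.** 28 + 6 = 34 and 56 + 6 = 62. Both match exactly.

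**The other limits between post-baseline visits in Table 6.7: 1**
- Week 4 / Week 8: (29 + 57)/2 = 43; the SAP uses 43.
- Week 8 / Week 12: (57 + 85)/2 = 71; the SAP uses 71.
- EOT / FU1: (0 + 28)/2 = +14; the SAP uses +14.

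In each case the midpoint day itself goes to the earlier visit. The treatment-period limits in Table 6.7: 3 (11, 22, 40, 53, 70, 84) also lie at or within half a day of their midpoints (11.5, 22, 39.5, 53.5, 70, 84).

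**The same rule applied to follow-up**
- FU1 / FU2: (28 + 56)/2 = +42; the SAP uses +34, which is 8 days earlier.
- FU2 / FU3: (56 + 84)/2 = +70; the SAP uses +62, which is 8 days earlier.

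The FU2 window runs from 56 − 35 = 21 days before its planned day to 62 − 56 = 6 days after it.

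**A visit at +35.** Distance to FU1: 35 − 28 = 7 days. Distance to FU2: 56 − 35 = 21 days. It is 1 day outside FU1's protocol window (22 to 34) and 15 days outside FU2's (50 to 62), yet it is filed under FU2.

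**Assignment of hypothetical visit dates**

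| Actual visits | SAP limits (34, 62) | Midpoint limits (42, 70) |
|---|---|---|
| FU1 +34, FU2 +56, FU3 +84 | all correct | all correct |
| FU1 +35, FU2 +56, FU3 +84 | FU1 empty; FU2 window holds +35 and +56, closest is +56 | all correct |
| FU1 +35, FU2 missed, FU3 +84 | FU1 empty; +35 reported as FU2 | FU1 correct, FU2 missing |
| FU1 +28, FU2 +63, FU3 +84 | FU2 empty; FU3 window holds +63 and +84, closest is +84 | all correct |
| FU1 +28, FU2 +63, FU3 missed | FU2 empty; +63 reported as FU3 | FU2 correct, FU3 missing |
| FU1 +35, FU2 +63, FU3 +91 | FU1 empty; FU2 shows +35; FU3 window holds +63 and +91, closest is +91 | all correct |

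Where a window holds two values, the one further from the planned day is left out for efficacy and vital signs. For laboratory and ECG data both compete and the worse one is used.

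**Displacement when a late value stands in for the next visit.** FU1 at +35 to +42 shown as FU2: 56 − 35 = 21 down to 56 − 42 = 14 days. FU2 at +63 to +70 shown as FU3: 84 − 63 = 21 down to 84 − 70 = 14 days.

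**The case against.** The SAP nowhere states a midpoint rule. Its windows leave no gaps, so every follow-up value maps to some visit, and where to cut is partly convention. Tables 6.7: 2 and 6.7: 3 do not use the midpoint at the end of Week 12 either: they close that window at +1, not +14. All of this stands, so the case cannot rest on a rule used throughout the SAP. It rests on the SAP's stated aim and on the other limits in Table 6.7: 1. Convention also does not explain a window that reaches 21 days back and 6 days forward.

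The consequences are also modest. Individual values stay in the listings (SAP Section 7). Clinically relevant laboratory and vital-sign findings are analysed as adverse events (SAP Sections 7.8.2 and 7.8.3). The laboratory reference-range tables use the last post-treatment follow-up rather than FU1 and FU2 separately. An abnormal late laboratory value remains visible under the worst-value rule, though under a later label.

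A reader might infer from COVID-19 that many visits are affected. SAP Section 4 says only that visits of several patients could be affected. Protocol Section 6.2.3 substitutes a phone contact when a site visit is impossible, and a phone contact produces no image or sample to misfile.

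**Conclusion.** The inconsistency is real and minor. Values from FU1 visits at +35 to +42 and FU2 visits at +63 to +70 are assigned to the next visit although they are nearer their own planned day, with a tie at +42 and +70. The damage is to descriptive by-visit follow-up summaries.

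Four stronger readings are not supported:
- **Any late visit is misfiled.** Visits at +29 to +34 and +57 to +62 are assigned correctly. The problem starts 7 days after the planned day, one day past the tolerance.
- **Changes appear four weeks late.** Four weeks is the spacing of the visit labels. For visits 7 to 14 days late the displacement is 14 to 21 days.
- **The main endpoints are affected.** Ocular and non-ocular adverse events are counted over the whole on-treatment period without these windows. The DRSS secondary endpoint is at Week 12, whose efficacy window ends at the midpoint.
- **Empty visits become treatment failures.** SAP Section 6.6 does say that "patients with missing data in the study eye at the time point of interest will be considered non-responders", but this matters only if a binary efficacy endpoint is analysed at a follow-up visit. The only visible route is the exploratory logistic model in SAP Section 7.5.2, which reports odds ratios by time point if enough patients respond. SAP Section 4 expects no more than 3 responders.

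The documents do not give the number of late visits, so the number of values affected cannot be calculated. The worked cases assume that the EOT dose is the last dose. The case where the next visit also took place assumes it was near its planned day, as Protocol Section 6.1 asks.

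**What to change.** Before database lock, in Tables 6.7: 1, 6.7: 2 and 6.7: 3:
- end FU1 at +42;
- run FU2 from +43 to +70;
- start FU3 at +71.

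Leave the FU1 start as it is in each table. Ties at +42 and +70 then go to the earlier visit, as they already do at Day 43, Day 71 and EOT +14.

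The cost is four cells in each of three tables, with the matching change to the window derivation in the analysis programs. No patient, site or data-collection step changes.
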